positive behavior changes to support health and wellness; forging strategies for improving diagnosis in dementia; charting the course of the disease; identifying risk factors; identifying potential avenues for treatment for individuals with a PPA diagnosis; and improving education for families faced with a PPA diagnosis as well as professionals who may treat them. Our speech-language pathologists have over 10 years of experience in treating hundreds of individuals with dementia. The project has the support of the Northwestern University Clinical and Translational Sciences (NUCATS) Institute, our CTSA-funded hub for supporting clinical and translational science. NUCATS will provide support for recruitment as well as data collection, data storage and data safety & monitoring.

We are confident about subject recruitment for this study since we enrolled 50 participants with PPA into our preliminary study over 3 years and currently have a waiting list for enrollment. Consistent with our goal to improve access to care, we expect >80% of the research participants for this project will reside out of town. In fact, 94% of the participants to date (n=47/50) came from outside of Chicago, residing in 21 different states, Canada and Singapore.

Study personnel include trained speech-language therapists and a licensed clinical social worker who will be able to intervene and recommend social, emotional, or psychological resources, if necessary. All of these individuals have worked extensively with individuals with PPA. They are all trained to identify and intervene in the event that a risk of self-harm, harm to others, and/or depression/anxiety is observed. Research assistants who collect data on the PROMIS anxiety/depression levels, are trained to alert the team (PI, therapists, social worker) if scores are above the normative range. Scores on this measure are converted to T-scores on REDcap. If a t-score indicates that the individual is over 1 standard deviation over the mean on depression/anxiety, the research team will be alerted and the Risk Plan will be followed as applicable.

PRIOR APPROVALS:

We have received a restricted notice of award from NIH to fund this project. Approval from our DSMB is required before we enroll participants into this study.

RECRUITMENT METHODS:

Recruitment sources will include Clinical Core participants at the Alzheimer's Disease Centers at Northwestern University (NU) and Oregon Health & Science University (OHSU), clinical referral (including NU and OHSU Clinics), Clinicaltrials.gov, NUCATS, the Alzheimer's Association TrialMatch website, as well as the Association for Frontotemporal Degeneration (AFTD).

Potential participants will be provided contact information of the research coordinator at the recruitment sources mentioned above. We will also have a recruitment flier, postcard, and brochure with information about the study available at these recruitment sources.

Additionally, we will have a Constant Contact email recruitment flyer that will be send out to individuals within Northwestern University and individuals on the CNADC mailing list.

Additional locations were recruitment fliers, postcards, and brochures may be handed out are academic conferences or lectures given by members of the study team.

If participants are eligible to participate in the study, they will be provided with a \$50 payment for their 1-year participation. This payment will come in the form of a check processed by Northwestern Accounting.

NUMBER OF LOCAL PARTICIPANTS:

n/a

CONFIDENTIALITY:

Data will be collected, entered, and stored securely on a REDcap

(www.redcap.nubic.northwestern.edu) database. The database will be password protected and accessible only to the principal investigator and study personnel. Paper copies of any measures will be kept in locked files in the Mesulam Center for Cognitive Neurology and Alzheimer's Disease. All video files will be stored on a locked computer and will be coded by study identity. Any names or identifying information will not be shared or disclosed. Only the PI and approved study personnel will be able to access these files.

PROVISIONS TO PROTECT THE PRIVACY INTERESTS OF PARTICIPANTS:

The consent form will list, in detail, who has access to medical records and personal identifiable information within the study team. Participants will be given the opportunity to ask questions and will be provided with a signed copy of their consent form.

Medical records will be sent to the study team by the participants, if they are not seen by a doctor affiliated with Northwestern Memorial Hospital. Individuals who saw Northwestern University doctors will consent to have their medical records shared with the study team for review. No one outside the PI or study team will have access to the medical records.

COMPENSATION FOR RESEARCH-RELATED INJURY:

The research study does not pose more than a minimal risk.

ECONOMIC BURDEN TO PARTICIPANTS:

Participants will have no expenses to participate in the study.

CONSENT PROCESS:

Participants (individuals with PPA and their communication partners) will be consented verbally over video-chat with a research coordinator. The consent forms will be housed within REDcap. During this video-chat consent, participants will have the study explained to them in detail and they will have ample time to ask for questions or clarifications. A research coordinator will go through the REDcap consent (sent via link to the participant) with the participants. The participants will electronically sign the consent forms. Participants will be emailed their signed informed consent from REDcap after completion of the form.

Participants (individuals with PPA and their communication partners) will be asked to consent to an optional element on the consent form that asks if they would be willing to allow their audio and/or video recordings from sessions to be used in scholarly presentations or publications. These recordings could potentially be shown at disease-related conferences and speech-language pathology professional conferences in order to help professionals in the field understand the research and/or aid in training purposes. Because of the unique and rare presentation of PPA, speech samples and/or video recordings that display the effortful motor movements in producing words are often the best way to convey how the disease presents itself. In order to thoroughly explain our research methods and describe the speech therapy strategies used, it will be most beneficial to provide audio and/or video recordings during presentations to explain what written or verbal text cannot accomplish. If the participant answers "I agree," he or she is indicating they understand the risks associated with identification.

Participants (individuals with PPA and their communication partners) will complete an optional section on the consent forms that asks if participants would be willing to share their data with other researchers at the CNADC. If the participant answers "yes", their data can be shared, if requested, from other researchers at the CNADC. This will not include identifiable information. Participants will initial whether they agree or disagree on the REDcap form via the electronic signature function in REDcap.

A Certificate of Confidentiality (COC) is in place for the current clinical trial and will be explained to participants during the consent process.

Cognitively Impaired Adults

Even though our participants have a cognitive impairment, they will be screened for eligibility prior to enrollment. At the mild stages of PPA, individuals have deficits in their affected language domain, but their other domains of language and cognition are relatively preserved. Additionally, participants will be consented into the study with a communication partner who can aid the research staff in clarifying any study components that are unclear. Our participants signed their own consent forms in the pilot study with no issues.

PROCESS TO DOCUMENT CONSENT IN WRITING:

Participants will be mailed a copy of the informed consent form. A research coordinator will administer informed consent over the video-conferencing program. Participants will mail their signed informed consent back to us in a prepaid envelope that is provided to them. A copy of the consent form will be mailed to the participants via postal mail or scanned via e-mail.

DRUGS OR DEVICES:

n/a

References

- 4. Mesulam MM. Primary Progressive Aphasia: A Language-Based Dementia. The New England Journal of Medicine. 2003;349:1535-1542

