- **Experimental Group.** Individuals in the experimental group will receive a person-centered intervention. A person-centered intervention includes a combination of therapy approaches to maximize functional communication and life participation. This intervention will include, but not be limited to, impairment-based strategies, compensatory strategies, communication partner training, and disease education. Communication partners will be required to attend all evaluation and therapy sessions over the course of the study.
- Control Group. Individuals in the control group will receive impairment-based treatment that will target areas of weakness in a rehabilitation approach to improve function of a specific cognitive domain. They will receive disease-education at the first treatment session. Communication partners will attend the first treatment session and a portion of subsequent therapy sessions.

Study Procedures

All evaluations and therapy sessions will take place over a HIPAA compliant videoconferencing program. All sessions will be video-recorded through this program.

Orientation and Training:

Participants and communication partners will undergo an orientation to the technological aspects of the study over two one-hour sessions. At the initial orientation, participants will be consented to the study, complete demographic questionnaires, and if randomized to the experimental group, they will be instructed on how to fill out the brainstorming form for their personally relevant words that will be targeted in therapy. After this session, the participant and communication partner will work on the brainstorming form while the research coordinator assembles and mails the participant laptop computer with a webcam and Ethernet plug, technology guides, and self-report questionnaires. Participants and communication partners are asked to complete their brainstorming form in a 3-week time period and return it to the study team.

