Post-Intervention Evaluation 2: This evaluation will be identical to the **Post-Intervention Evaluation 1** in Block 1. This evaluation will take place approximately one week following the 5 weekly therapy sessions of Intervention Block 2. Identical to other evaluations, this will occur over two sessions lasting no more than 2 hours per session (4 hours in total).

12- month Evaluation: Approximately one year after the Baseline Evaluation, the participant will take part in a final evaluation. Post-treatment outcomes will be measured through standardized evaluation measures, communication participation measures, and language performance measures that have been given throughout the course of the study. Identical to other evaluations, this will occur over two sessions lasting no more than 2 hours per session (4 hours in total).

Scheduling Compliance:

Sessions: To successfully complete the trial, participants must complete 10 visits within 12 weeks for the first treatment block and 5 visits within 7 weeks for the second treatment block. Circumstances may arise that require the re-scheduling of visits. When this occurs, the following rules apply:

- No more than 2 visits may be scheduled within a 5-day window
- Sessions on consecutive days should be avoided

Visits that cannot be scheduled within these rules will be considered 'missed' visits. In the case of a missed visit, the visit will not be re-scheduled. Dosing effects resulting from missed visits will be accounted for in the statistical analyses. Participants with more than 2 missed visits will be asked if they would like to continue to receive the intervention as part of routine clinical care; however, the participant will be withdrawn from the study analysis.

6-Month and 12-Month Evaluations: These evaluations should be scheduled within a time window that includes the 2-weeks prior to or following the actual 6 or 12 month follow-up date.

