Aim 1: Determine the within-group response of the Experimental and Control treatments for adults with PPA. Aim 1a will provide a descriptive and quantitative characterization of the response to treatment including within- group effect sizes.

Statistical analysis Aim 1a: The primary analysis goals for Aim 1a will be (i) the estimation of the within-person change and the variability in this change along with the statistical significance of the change within each treatment group and (ii) the estimation of the within-group effect size for each treatment group. These analyses will be done for all outcomes.

Power calculation for Aim 1: In preliminary data, the Pearson correlation between the initial and 6 month CCRSA was 0.70. Assuming a standard deviation of σ for an outcome at one time, and assuming a correlation of 0.50 between the initial and 12 month measure (since follow-up is longer), then the standard deviation of the change is also σ . Similar assumptions will be made for all outcomes. The Experimental group with a sample size of 51 would have 80% power to detect a mean change that is 0.4 σ while the Control group with a sample size of 34 would have 80% power to detect a mean change of 0.5 σ . For testing correlations between the change in an outcome and a continuous measure, the Experimental group (n=51) would have 80% power to detect a correlation of 0.38 while the Control group (n=34) would have 80% power to detect a correlation of 0.46. Two-tailed tests and a Type I error rate of 5% are assumed for all calculations for Aim 1.

Aim 2: Determine if a person-centered dynamic treatment approach (Experimental) for adults with PPA will show more favorable communication participation outcomes as compared to an impairment-only treatment approach (Control) over a 12-month course of disease.

Specific Aim 2 Analysis: The group statistical analysis will focus on two participation measures (CCRSA, Goal Attainment Scaling [GAS]) and two language performance measures (% target word accuracy and % script accuracy). All outcomes are continuous measures except for GAS which is ordinal. The primary analyses will focus on the initial and 12-month time points. Secondary analyses will be done using all time points, specifying certain post-hoc comparisons of interest (e.g. comparing the effect of the preand post-evaluations for the 6-month Treatment Sessions between groups).

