Power Calculation for Aim 2: Power will be based on a sample size of 51 in the Experimental arm and 34 in the Control arm. For all language and participation outcomes, preliminary data were used to estimate unadjusted standard deviations (SDs). It is expected that analysis of covariance would reduce the unadjusted SDs but since longitudinal data were not available on all measures, the conservative approach will be to use the unadjusted SDs in the power calculation. The Table below gives the between-group effect size (in units of the scale) detectable with 80% power for each outcome measure using a two-tailed test and a Type I error rate of 0.017. For example, for the CCRSA scale, there is 80% power to detect an Experimental minus Control difference of 12% in the 12-month mean adjusted by analysis of covariance for the initial evaluation CCRSA level.

Measure	Туре	SD	Between-group effect size with n=51 and 34 per arm ^A
Lexical Retrieval	Language	19 16	13
Script Performance	Language	14 25	10
Confidence Rating Scale for Aphasia (CCRSA)	Participation	16 16	12
Goal Attainment Scaling (T-Score)	Participation	10 26	7
^A 80% power, 2-tailed p<0.025 for language measures and $p<0.017$ for participation measures			

Table 1. Power Calculations

All members of the study team will be trained on the procedures of how data are stored and managed. Members of the study team that are approved by the Northwestern IRB will have access to the REDcap database and to the web-application database. All access to these applications will be provided over encrypted-TLS communication and all servers are locked and managed in a physically secure facility with Marlok identity management. All data will be de-identified and stored as much.

All data will be checked by a research assistant who is different from the individual who administered the tests. This checking will take place on hard copies of outcome measures and data stored in REDcap. Discrepancies between raters will be recorded by a crossing out of original score and initialing the new score with the checkers initials. REDcap includes a feature where data can be marked as "unchecked" or "checked". Once data are checked by a second scorer, they will be marked as "checked" in REDcap.

Participants will be asked if they are willing to share data from the study with other researchers within the CNADC. If so, researchers will not receive any identifiable information.

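### The commitment to account for missed-visit dosing is not kept out of the primary Aim 2 comparison; an attendance covariate there could bias the arm difference in either direction

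*Combined protocol and SAP*

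**What the plan says.** Three parts of the combined protocol and SAP bear on this.

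- **Scheduling Compliance (Procedures Involved).** After defining a missed visit, the text states: "Dosing effects resulting from missed visits will be accounted for in the statistical analyses". The next sentence deals with people who miss more than 2 visits. They may be offered continued treatment as routine care, "however, the participant will be withdrawn from the study analysis".
- **Specific Aim 2 Analysis and Power Calculation for Aim 2.** "The primary analyses will focus on the initial and 12-month time points". The only covariate named is the starting value: the CCRSA example refers to the "12-month mean adjusted by analysis of covariance for the initial evaluation CCRSA level". No attendance or dose term appears, and none is ruled out. No intention-to-treat set is defined.
- **Experimental Group and Control Group.** In the experimental arm, "Communication partners will be required to attend all evaluation and therapy sessions over the course of the study". Control partners come to the first treatment session and to part of the later ones.

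The aims do name a compliance measure, in Aim 1b, but it is completion of home exercises, not visits. The dosing sentence therefore cannot simply be read as pointing to Aim 1b.

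**The concern.** The number of sessions attended is a consequence of what happens after randomisation. It may depend on the arm, because the two arms ask different amounts of the communication partner. It may also depend on how fast the participant declines. A covariate with both properties does two things in a between-arm model. It removes any part of the treatment effect that works through attendance, and it compares people with equal attendance who may differ in unmeasured prognosis.

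An analyst who follows the dosing sentence literally could add missed visits to the Aim 2 model, and the choice could be made after the data are seen. At stake is whether the Aim 2 contrast still estimates the effect of being assigned person-centred treatment, and whether its Type I error stays at the planned level.

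**Working it through.** **1. The plan's own figure.** Inputs are from Power Calculation for Aim 2: "Power will be based on a sample size of 51 in the Experimental arm and 34 in the Control arm"; a "two-tailed test and a Type I error rate of 0.017"; 80% power; CCRSA SD 16 (the second 16 in that table cell is read as a citation number).

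Detectable difference = (z for 0.017 two-sided + z for 80% power) × SD × √(1/51 + 1/34) = (2.387 + 0.842) × 16 × 0.2214 = 11.44. A noncentral t calculation with 83 df gives 11.64, which rounds to the stated 12. The figure reproduces, and it does not depend on the dosing sentence.

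**2. Why the covariate moves the estimate.** In least squares,

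arm coefficient with missed visits = arm coefficient without − (coefficient of missed visits) × (arm difference in missed visits, given the initial level).

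Under a true null the coefficient without the term averages 0. The shift is therefore zero if the arms miss equally, and zero if missed visits do not predict outcome. Otherwise its sign follows which arm misses more.

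**3. Size under assumptions.** From the plan: 51 and 34 participants, SD 16, two-sided alpha 0.017, and correlation 0.50 between initial and 12-month values (Power calculation for Aim 1). **Not in the documents and assumed here:** mean missed visits per arm; Poisson counts; an unmeasured decline factor that raises the absence rate by 65% per SD and lowers the outcome by 0.4 SD (0.5 SD in the second scenario); no true treatment or dose effect; full 12-month follow-up. ANCOVA on the initial level, everyone analysed:

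| Missed visits, exp. vs control | Link to outcome | Bias without dose term | Bias with dose term | Type I error with dose term |
|---|---|---|---|---|
| 1.9 vs 1.1 | 0.4 SD | about 0 | about +1.7 | about 3% |
| 2.3 vs 1.1 | 0.5 SD | about 0 | about +3.0 | about 7.5% |
| 1.1 vs 1.9 | 0.4 SD | about 0 | about -1.8 | not tabulated |
| equal | 0.4 SD | about 0 | about 0 | nominal |

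Without the dose term, Type I error is about 1.7%. The identity in step 2 explains the sizes: 1.7 / (1.9 − 1.1) = 2.1 and 3.0 / (2.3 − 1.1) = 2.5 CCRSA points per missed visit.

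**4. With the plan's exclusion applied first.** Counting visits over both blocks, the assumed rates remove about 29% of the experimental arm and 12% of control in the first scenario, and 38% and 12% in the second.

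| Scenario | Exclusion alone | Exclusion plus dose term | Added by dose term |
|---|---|---|---|
| 1.9 vs 1.1 | +1.1 (about 2% Type I error) | +1.7 (about 3%) | 1.7 − 1.1 = 0.6 |
| 2.3 vs 1.1 | +2.0 (about 4%) | +3.0 (about 6%) | 3.0 − 2.0 = 1.0 |

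**5. A second attendance model.** Here missed visits are binomial out of 15, with log-odds slope 0.7 per SD of a latent prognostic factor that explains half the residual variance. With everyone analysed, the dose term gave +2.5 points (1.9 vs 1.25 missed), +5.4 (2.8 vs 1.25), -2.0 (0.8 vs 1.25) and -3.5 (0.5 vs 1.25). It gave about 0 when attendance was equal or unrelated to prognosis. After the exclusion, the dose term added 2.4 − 1.5 = 0.9 and 5.2 − 3.7 = 1.5 in the first two cases. The mechanism is the same; the size depends on the assumptions.

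**The case against.** The strongest reply is that the plan never says attendance enters the Aim 2 model. Accounting for dose could mean a within-arm analysis, a sensitivity analysis or a table. The Aim 2 text names only the initial level, and the Aim 1 power text already provides for within-arm correlations between change and a continuous measure, a natural place for a dose analysis. This stands: a reader might infer that the plan conditions Aim 2 on attendance, but the documents support only that it leaves this open.

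A reader might also infer a tilt towards Hypothesis 3, because experimental partners must attend every session. The documents do not support a direction. They give no missed-visit rates, partners in both arms have to be scheduled, and participants confirm their availability at enrolment, with the start delayed if necessary. If the control arm misses more, the bias goes against the experimental arm.

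Third, the exclusion after more than 2 missed visits is the explicit post-allocation conditioning. It accounts for about two-thirds of the simulated bias in the main scenarios (1.1 of 1.7 and 2.0 of 3.0), and it leaves only 0 to 2 missed visits for a dose term to act on. This also stands, and it is why the two rules should be corrected together. It does not dispose of the point, because the dose term still adds bias among those retained.

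**Conclusion.** The point holds as an unrestricted commitment that could be applied to the primary Aim 2 comparison, not as a stated model. If it is applied there, the arm coefficient ceases to estimate the effect of assignment. Bias needs both unequal attendance and a link between attendance and prognosis, and its sign follows the arm that misses more.

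Under the main assumed scenarios, the shift with everyone analysed is roughly 14% to 25% of the detectable difference of 12 (1.7/12 and 3.0/12). The increment over the plan's own exclusion is 5% to 8% of it (0.6/12 and 1.0/12). These are illustrations: the attendance gaps and prognostic links are not in the documents. The case for acting rests on an open choice in the primary analysis that is nearly free to close, not on a demonstrated bias.

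**What to change.** Add to the Aim 2 analysis text, in substance: the primary Aim 2 model contains randomised arm and baseline covariates only, with no attendance covariate, and analyses all randomised participants with available data by assigned arm. State that dose-response for sessions attended is a secondary, non-randomised analysis within each arm, and name its method. Tabulate sessions attended by arm.

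Reconcile Scheduling Compliance, which removes people from the analysis, with Withdrawal of Participants, which uses data up to lost contact. Those sections also differ on the trigger: more than 2 missed visits in one, no-shows for two sessions without rescheduling in the other. Say whether missed visits are counted per block or in total. Which treatment or withdrawal rule applies is for the investigators; the analysis set should not depend on it.

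Cost: one or two SAP sentences and one table. No stated sample size or power figure changes, and the dose analysis is kept.
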